Areas of the bone surrounding the implanted device which show low density lines or rounded areas are considered radiolucencies which may indicate areas of potential concern. While radiolucencies can be found in well fixed, asymptomatic total hip replacements, the chance of loosening increases with the extent and thickness of radiolucent areas at the bone-implant interface. In particular, implants with radiolucent areas which appear as continuous gaps around the implant greater than or equal to 2 mm in width have the highest probability of loosening. Radiolucencies observed in varying shapes indicative of localized bone resorption, cystic erosion, increased shear stress, and diffuse linear forms are normally considered to result from expansion of the periprosthetic cortical bone.

Areas of radiolucency in linear form in the zones around the implanted device will be measured and reported, irrespective of root cause (lesions, resorption, shear stress, etc.). Each zone (Figures in CRF above) will be evaluated for radiolucencies and the maximum width of the radiolucent line measured will be noted in whole mm using standard rounding rules (≥2 mm is considered significant). Any observed radiolucencies will be tracked longitudinally.

Osteolysis:

Osteolysis is the dissolution of bone through the active resorption of native bone matrix by osteoclasts as a result of disease, infection, or ischemia. The development of periprosthetic osteolysis is not an uncommon occurrence following joint replacement and is believed to be a secondary response of macrophage activity stimulated by microscopic wear particles released from articulation of components in an artificial hip joint.¹¹ The resulting biological cascade promotes progressive bone degeneration leading to implant loosening or fracture. While originally associated with cemented components, periprosthetic osteolysis has also been demonstrated with non-cemented devices of various materials¹¹ such as ceramics, polyethylene, and metals. In particular components consisting of ultra-high molecular weight polyethylene have shown higher incidence of osteolysis due to increased wear debris.¹² Regardless of the etiology, distinguishable osteolysis or resorption will be documented on the case report form according to the zones in which changes are observed.

All radiographs are to be reviewed for evidence of osteolysis. The presence of osteolytic lesions will be noted on the case report form according to zonal areas involved. The maximum width of the lesion will be noted in whole mm using standard rounding rules. Osteolytic lesions may form in localized areas surrounding the implant shaped as linear, cystic, or expansile regions. AP-pelvis, AP-hip and lateral radiographs are to be reviewed for evidence of osteolysis. If an osteolytic lesion is found, subsequent radiographic evaluations should be used to determine whether the lesions are stable or progressive to help characterize prognosis for implant survival (include in the "Notes" section of the CRF).

Atrophy:

Cortical bone thinning (atrophy) is associated with bone loss. Adaptive atrophy commonly occurs with cementless components in the superomedial acetabulum and the proximal medial femur as a result of stress shielding. The extent in millimeters and location of bony atrophy should be recorded using the zonal map.

Hypertrophy:

Cortical hypertrophy often occurs as a result of increased stress loading. The extent in millimeters and location of bony hypertrophy should be recorded using the zonal map.

References

- 2. Conza, N (2008) Assessment of acetabular orientation from anterior-posterior X-ray pelvic overviews. Technical Report, Smith & Nephew
- O'Neill, DA, & Harris, WH. (1984, April). Failed Total Hip Replacement: Assessment by Plain Radiographs, Arthrograms, and Aspiration of the Hip Joint. *Journal of Bone and Joint Surgery*. 66-A: 540-546.

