7.4. Postoperative Follow-up Evaluations

Subjects will be seen at the 3 months, 1 year, 3 years, 5 years, 7 years and 10 years interval post surgery. The Harris Hip Score will be collected and the HOOS and UCLA questionnaire obtained at each visit.

Anteroposterior (AP) and (shoot trough) lateral radiographs of the operated hip will be taken before discharge in addition to at 1 year, 3 years, 5 years, 7 years and 10 years postoperatively. At least the 1 year follow-up radiograph should include full pelvic overview (including at least 20 cm of the proximal femur). Pelvic AP radiograph will be used for analysis of cup inclination and leg length discrepancy.

Postoperative radiographs will be taken to determine component alignment, radiolucencies^{20,21}, and bone condition. The alignment of the femoral prosthesis will be measured as the angle between the central axes of the proximal femoral canal and the femoral prosthesis. Angles will be classified as varus, valgus or neutral²². The angle of the acetabular cup will be

Smith & Nephew - Confidential/Study ProtocolR3H01/01Feb2017/Version2.0/BNA including PAS

assessed by measuring the angle of vertical tilt of the acetabular cup (angle between a line joining the ischial tuberosities and one through the long axis of the ellipse of the acetabular cup)²³. Additionally, the cup anteversion will be recorded. Observations will be recorded on the x-ray case report form and independently reviewed.

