- If more than one copy of a particular AP or lateral scan is available, the independent radiologist will select the best quality scan for assessment
- If the radiographs are missing or have poor quality such that a reasonable assessment cannot be made, a substitute radiograph acquired immediately before or after the particular time point (+/- 6 months) may be used if available. If not, the scan/time point will be treated as unavailable.

- If an AP or lateral view film is available but has a portion that is of poor quality or under/over-exposed such that a reasonable assessment is not possible, then the obscured AP or lateral radiographic zone affected will be left blank or marked as "NA" in or next to the appropriate corresponding fields on the case report form.
- Lauenstein radiographs may be used when lateral radiographs are not obtained or available.
- AP hip may be used at Year 1 as a substitute for AP pelvis when the AP pelvis was is obtained or unavailable in order to ensure partial information is collected
- AP pelvis may be used at all time points as a substitute for AP hip when the AP hip is not obtained or is unavailable.

Discharge Time Point: Independent Review Immediate Postoperative CRF

At the discharge (immediate postoperative) time point, AP hip and lateral images will be used to assess cup position and femoral stem position. The CRF fields are shown below.

Cup position	Stem position	
· · · · · · · · · · · · · · · · · · ·	(Tick one box only)	
	neutral	
	☐ varus	
	☐ valgus ☐	

Cup position:

- Cup position at discharge will be estimated using lateral inclination.
- The location of the contralateral ischial tuberosity will be estimated and the transischial tuberosity line drawn
- Orientation of the acetabular cup will be assessed by measuring the angle formed by a line along the
 lateral margin of the acetabular component intersecting the estimated transischial tuberosity line
 (Figure 5, "Inc"). The inclination angle of the acetabular cup is determined by drawing a tangential
 line to the face of the prosthesis and a second line drawn through the roentogenographic teardrop
 landmarks.
- Using a digital tool, measurement of the subtended angle of the two lines determines the amount of inclination of the prosthesis.
- Normal acetabular inclination is between 30 and 50 degrees
- Acetabular inclination at each follow up time point will be compared to the discharge time point

Femoral Stem Orientation:

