Noticeable settling or sinking of a prosthesis component into the bone following total joint implantation is known as subsidence or migration and may result in loosening and eventual failure of the implant. The amount of subsidence may vary in severity from subtle changes of the bone to actual movement of the device from the original fixation position. A discernable shift or migration can occur in either the acetabular component or the femoral component. Implant positions relative to various landmarks on both the baseline post-operative and post-operative radiographs will be used to determine subsidence according to the methods described by Sutherland, Wilde, Borden, & Marks.⁴

Using standardized reference points (see **Figure 4** below), migration of the acetabular cup and femoral component will be reported in whole millimeter increments. Standard rounding rules will be used to round the nearest millimeter.

Comparison measurements of the prosthesis are sensitive to patient position, x-ray techniques, and image magnifications. Due to the inherent variability in radiographic measurements, only changes ≥ 5 mm are to be considered to be significant and evidence of migration or subsidence. All measurements will be reported as a change with respect to discharge cup and stem locations. Thus, to ensure consistency in landmark selection discharge scans must be evaluated simultaneously with each follow up time point.

Acetabular Inclination measurement:

- The AP pelvis view will be used to evaluate acetabular inclination/tilt.
- Acetabular angular motion will be reported as a change in acetabular cup inclination with respect to discharge cup inclination, thus corresponding discharge scans must be viewed in conjunction with the current time point
- Inclination of the acetabular cup will be assessed as described above by measuring the angle formed by a line along the lateral margin of the acetabular component intersecting the bi-ischial line (Figure 5, "Inc"). The inclination angle of the acetabular cup is determined by drawing a tangential line to the face of the prosthesis and a second line drawn through the roentogenographic teardrop landmarks.
- Using a digital tool, measurement of the subtended angle of the two lines determines the amount of inclination of the prosthesis.
- Normal acetabular inclination is between 30 and 50 degrees
- Differences in acetabular inclination less than 4 degrees are not considered significant.

Femoral Stem Position measurement:

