- Orientation at each follow up time point will be reported as a change with respect to the discharge timepoint; corresponding discharge radiographs must be viewed simultaneously with each follow up time point
- Orientation will be classified as neutral, varus or valgus.
- Assessment will be made by measuring the angle between the lateral surface of the shaft of the femurand the longitudinal axis of the femoral component through the center of the medullary canal.
- If varus or valgus, the measured angle will be recorded in whole degrees on the CRF.

Femoral Subsidence measurement:

- Changes along the vertical axis will be determined by referencing the superior tip of the greater trochanter to the center of the femoral head and the vertical distance from the most inferior margin of the shoulder of the femoral component to the most proximal point on the lesser trochanter. See **Figure** 4 for femoral landmarks.
- Measurements will be reported as a change with respect to discharge stem location thus corresponding discharge radiographs must be viewed simultaneously with each follow up time point.

Acetabular Cup Subsidence measurement:

- Acetabular migration assessment will be performed on the AP pelvic image (Fig 5 above).
- Acetabular cup migration (subsidence) will be reported as a change in the measured distance along the vertical or horizontal axis in relationship to the hip center (HC) of the acetabular component
- The center of the acetabular component will be used as a standard reference point. The Kohler (K, blue) line, drawn from the pelvis along the medial aspect of the ilium and ischium will be used as a landmark in relation to the HC to determine movement along the horizontal axis (SH, red line).
- Vertical movement (SV, orange line) will be the shortest distance between the HC and a horizontal line from the inferior aspect of the teardrop (T).
- As with the femoral subsidence described above, it is difficult to eliminate all errors from positioning thus measured changes in relationship to referenced landmarks less than 5 mm are not considered significant for acetabular cup migration.⁴
- Measurements will be reported as a change with respect to discharge acetabular cup location thus corresponding discharge radiographs must be viewed simultaneously with each follow up time point

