Although the AP pelvic image is preferred for determining migration, if the image is not available or is of poor quality, the AP hip view may be used to determine cup migration. In the AP hip image, a reference to the horizontal axis will be used to measure the horizontal distance between the midpoint of the lateral edge of the metal shell and a line drawn through the center of the teardrop. Movement along the vertical axis will be determined by measuring the distance from the midpoint of the edge of the metal outer shell to a line tangent to the inferior edges of both teardrops on the AP pelvic view.

Stem Fixation:

Stem fixation - uncemented stems (Engh et al)
not applicable
fixation by bone ingrowth
stable fibrous ingrowth
unstable implant

[figure not shown]
Only uncemented stems will be used in this study. There are three options for stem fixation assessment: fixation by bone ingrowth, stable by bone ingrowth, and unstable implant. Further definition of each of these terms follows:

- Fixation by bone ingrowth
 - Spot welding (new bone formation contacting the prosthesis) and absence of lucent lines next to porous coating
- Stable fibrous ingrowth:
 - Unchanged radiolucent lines at bone-metal interface measuring <2 mm in width, often associated with a sclerotic line
- Unstable implant
 - Progressive increase in radiolucent lines at the bone-metal interface, component migration, or pedestal formation (bony hypertrophy around tip due to stress loading)

Heterotopic Ossification:

Hete	erotopic ossification (Brooker Classification) (Tick one box only)
	Grade 0 none, no islands of bone
	Grade I islands of bone within the soft tissues about the hip
	Grade II bone spurs from the pelvis or proximal end of the femur leaving at least 1 cm between opposing bone surfaces
	Grade III bone spurs from the pelvis or proximal end of the femur, reducing the space between opposing bone surfaces to less than 1 cm
П	Grade IV apparent bone ankylosis of the hip

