3.5.2 Secondary efficacy endpoints

Secondary endpoints will be evaluated at 10 years post study procedure and include the following:

- Patient outcomes as measured using the modified Harris Hip Score;;
- Radiographic evaluation to assess radiographic success defined as:
 - -No radiolucencies greater than 2 mm in 50% or more in any of the cup or stem zones; and
 - -No femoral or acetabular subsidence greater than or equal to 5mm from baseline; and
 - -No acetabular cup inclination changes greater than 4 degrees (4°);

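### On an AP hip film alone, cranial cup migration has no reference line that can be drawn as written, and the plan does not require one measurement method at discharge and follow-up

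*Combined protocol and SAP*

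**What the plan says.** SAP section 3.5.2 makes this one condition of radiographic success: "No femoral or acetabular subsidence greater than or equal to 5mm from baseline". A second condition limits the change in cup inclination to 4 degrees.

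The Image Evaluation Protocol, under Acetabular Cup Subsidence measurement, gives the preferred method: "Acetabular migration assessment will be performed on the AP pelvic image". Migration is measured "in relationship to the hip center (HC) of the acetabular component", horizontally against the Kohler line and vertically against a horizontal line at the lower teardrop. If the pelvic film is unavailable or poor, the AP hip film may be used. The horizontal distance is then taken from "the midpoint of the lateral edge of the metal shell" to a line through the centre of the teardrop. The vertical distance is taken from the midpoint of the shell edge to "a line tangent to the inferior edges of both teardrops on the AP pelvic view".

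On which films exist, main protocol section 7.4 schedules AP and lateral films of the operated hip at discharge and at 1, 3, 5, 7 and 10 years. On the pelvic view it says: "At least the 1 year follow-up radiograph should include full pelvic overview". For the discharge baseline the Image Evaluation Protocol says: "AP hip and lateral images will be used to assess cup position and femoral stem position". Its substitution rules let an AP pelvic film replace an AP hip film at any time point.

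Inclination is defined first against the bi-ischial line and then, in the same bullet, against "a second line drawn through the roentogenographic teardrop landmarks".

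**The concern.** The fallback applies when the pelvic film is missing, yet its vertical axis is defined on that film. A reader holding only an AP hip film must improvise a line or leave cranial migration unassessed.

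There is a second, separate problem. Every migration value is a change from discharge. Discharge is planned on AP hip, while the preferred follow-up method is on AP pelvis, and the two views carry different landmarks. A difference between them need not be movement of the cup.

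At stake are the cup-subsidence component of radiographic success and, through the double definition of inclination, the inclination component. A cranial field left unassessed could also enter the SAP section 4.4 sensitivity analysis that counts missing data as failures. A wording gap would then look like a device outcome.

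**Working it through.** The plan states no figure to reproduce here. The check compares the texts and adds one geometric illustration.

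**1. The two methods side by side** (Image Evaluation Protocol, Acetabular Cup Subsidence measurement)

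| Element | AP pelvic film | AP hip fallback |
|---|---|---|
| Point on the cup | Hip centre of the component | Midpoint of the shell edge |
| Horizontal reference | Kohler line | Line through the teardrop centre |
| Vertical reference | Horizontal line at the lower teardrop | Tangent to both teardrops, on the pelvic view |

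The fallback's horizontal distance needs one teardrop and the shell, so it can be drawn on an AP hip film. Its vertical distance names a view that is absent. The discharge instructions have the reader estimate the contralateral ischial tuberosity on the AP hip film, so the plan does not expect that film to show contralateral landmarks. No similar estimate is offered for the second teardrop.

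**2. How often the schedule permits this**

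Imaging time points: discharge, 1, 3, 5, 7 and 10 years, which is 6. A pelvic view is required at 1 year only. Time points where an AP hip film alone satisfies the schedule: 6 − 1 = 5, namely the discharge baseline and 4 of the 5 follow-up visits. This counts what is permitted, not films actually obtained.

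**3. How far apart the two cup points could lie**

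Assumptions:
- Shell diameter is 50 to 68 mm. This is the range the main protocol introduction gives for metal inserts; no sizes are stated for the ceramic-on-ceramic cohort.
- The shell is hemispherical, as the Image Evaluation Protocol says.
- Inclination is 30 to 50 degrees, its normal range.

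Reading A: the landmark is the superolateral rim point. The vertical offset from the cup centre is R × sin(inclination) and the horizontal offset is R × cos(inclination).

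| R (mm) | Inclination | Vertical (mm) | Horizontal (mm) |
|---|---|---|---|
| 25 | 30° | 12.5 | 21.7 |
| 25 | 50° | 19.2 | 16.1 |
| 34 | 30° | 17.0 | 29.4 |
| 34 | 50° | 26.0 | 21.9 |

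Reading B: the landmark is the midpoint of the opening face. For a hemisphere that is the centre, so the offset is about 0 mm.

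The wording therefore admits offsets from about 0 to 29 mm, against a threshold of 5 mm. If both films use the same landmark and the cup has not tilted, the offset cancels. It enters a change value only when the methods are mixed. The horizontal references differ under either reading, and the documents give no distance between the Kohler line and the teardrop line.

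**4. Inclination**

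The two reference lines appear in the same bullet at discharge, at 1 year and at later follow-up. The ambiguity is therefore the same at every visit: the text does not say which line governs.

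**The case against.** The strongest reply is that the gap is narrow and the plan already contains safeguards. The reader must view the discharge film with each follow-up film so that landmarks are chosen consistently. The discharge form has fields for cup and stem position but none for a migration distance, so the baseline distance can still be taken with the follow-up landmark. Fields that cannot be assessed are marked as such, and the views used are recorded. Figures 4 and 5, which show the reference points, are not visible here and may clarify some landmarks.

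Much of this stands. Mixing landmarks is something the text permits, not something it prescribes. But an instruction to be consistent does not say which method governs when the two films are different views. Nor can a figure supply a line that the words place on an absent film.

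Three stronger readings are tempting and not supported:
- A reader might infer that acetabular subsidence cannot be measured at most visits. Only the vertical fallback fails. Section 7.4 sets a minimum for pelvic views, the substitution rules allow them at any visit, and actual film counts are not given. A pelvic film that is only partly poor may still show both teardrops.
- A reader might take the offsets of 12.5 to 29.4 mm as the expected error. They depend on one reading of an undefined landmark and on shell sizes not stated for this cohort.
- A reader might infer that inclination will often be unobtainable. The discharge instructions show how an angle can be estimated on an AP hip film, and the wording does not vary by visit.

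**Conclusion.** The point holds in limited form. At any visit with only an AP hip film, cranial cup migration cannot be measured as the Image Evaluation Protocol is written. The schedule allows this at 5 of 6 imaging time points, including baseline. Medial migration can be measured there.

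Separately, a change judged against 5 mm may compare unlike quantities, because cup point and horizontal reference depend on the view and one method is not required across the pair of films. The size of that error is unknown. The offset range of about 0 to 29 mm shows that the landmark needs defining; it does not estimate bias. The inclination instruction has a smaller defect of the same kind.

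The consequence is confined to components of a secondary endpoint that SAP section 7.2 summarises descriptively. Implant survivorship at 10 years, the primary endpoint, does not use these measurements. The correction should be made before the 7- and 10-year films are read, which the Image Evaluation Protocol leaves to a new statement of work.

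**What to change.** Amend the Image Evaluation Protocol as follows:
- Reword the fallback so that its vertical reference uses landmarks visible on the AP hip film. State both the landmark and how the horizontal direction is set, since one teardrop gives a point and not a line.
- Define the shell-edge midpoint in words.
- Require each change value to use the same landmarks and method on the discharge and follow-up films, re-measuring the discharge film where needed. Record the method as well as the view. Where this cannot be done, mark that field not evaluable.
- Name one reference line for inclination.

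The Kohler-line method can stay where both films are pelvic views. Replacing it throughout would mean re-measuring follow-up films already read or contracted through year 5.

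The cost is the rewording and re-measurement of some discharge films, plus any earlier angles read against an inclination line other than the one chosen. No new radiographs or readers are needed.
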